1.3.2 Neuroprotective Effects of Progesterone

Progesterone is classified as a neurosteroid. The enzymes necessary for its synthesis are present in the brain and the progesterone receptor is widely distributed in the forebrain, limbic system and hypothalamus early in development.⁷ The potential neuroprotective effects of progesterone were discovered because of sex differences in recovery from experimental brain injury. Progesterone is neuroprotective in animal models of stroke. Administration of progesterone prior to middle cerebral artery occlusion decreases infarct size.⁸ Post-ischemic administration has also been shown to reduce injury. Progesterone reduces cerebral edema after experimental TBI.⁹ Progesterone also has a positive effect after spinal cord contusion.¹⁰ Following peripheral nerve injury, progesterone administration has been shown to induce re-myelination.¹¹ There is growing evidence, including recently published clinical trials, that progesterone and its metabolite allopregnanolone exert neuroprotective effects on the injured CNS in humans.¹² These positive effects include not only decreased mortality, but also reduced morbidity and improved functional outcomes.¹³⁻¹⁵

A recent Cochrane review evaluated all randomized controlled trials looking at the effects of progesterone in people with TBI.¹⁶ The review focused on randomized controlled trials in which, in addition to standard treatment, the experimental group received progesterone and the control group received non-active treatment (placebo) or no additional treatment. The authors identified three studies with a total of 315 subjects. There was evidence of a beneficial effect of progesterone on mortality and disability after TBI. Subjects in the progesterone group had a risk of death around 40% lower than those in the control group.

The results of this review indicate that progesterone may reduce mortality and disability compared to the control group with no additional adverse events.

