5.1.6 Other Evaluations, Measures

Neonatal Admission Questionnaires

Demographic, Ethnicity and Socioeconomic Status (SES) Forms: demographic information will be collected in order for the study team to maintain contact for 18-month follow-up. In addition self-report ethnicity, level of education, and type of employment will be

obtained on both mother and father. This information will serve as data to calculate the Hollingshead score, a measure of SES.

Maternal and Cord Blood Tests

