5.2 Efficacy Evaluations

5.2.1 Obstetric Ultrasound

The ultrasound examination will be conducted with real-time scanners, using a transabdominal or a transvaginal approach or both. All examinations will be performed by one of three experienced perinatal sonographers using the same ultrasound equipment, who will be blinded to the patient group assignment. The abdominal and transvaginal transducers to be used will include frequencies ranging from 3 MHz to 10 MHz or higher to provide superior resolution while allowing adequate penetration. The detailed obstetric ultrasound examination to be performed at the initial evaluation will include cardiac activity, fetal presentation, amniotic fluid index (AFI), placental position, fetal biometry, an anatomic survey. The maternal cervix (normal, funneled, short or long (in centimeters) and adnexa will also be examined (presence, location and size of uterine or adnexal masses).

Cardiac activity: fetal heart rate and rhythm.

Fetal presentation: cephalic, breech, transverse or variable.

Amniotic fluid index: less than 5 cm, oligohydramnios and more than 24 cm, polyhydramnios or deepest amniotic fluid vertical pocket (less than 2 cm, oligohydramnios and more than 8 cm, polyhydramnios).

Placental position: anterior, posterior, fundal, lateral, low-lying or previa.

Placental cord insertion: central, marginal, eccentric, velamentous.

Fetal Biometry at initial Examination:

- Biparietal diameter (BPD) will be obtained at the level of the thalami and cavum septi pellucid, and the measurement will be taken from the outer edge of the proximal skull to the inner edge of the distal skull.
- Head circumference (HC) will be measured at the same level as the BPD, around the outer perimeter of the calvaria.
- Femoral length (FL) and humeral length (HL) will be measured with the beam of insonation perpendicular to the shaft, excluding the distal femoral or humeral epiphysis.
- Abdominal circumference (AC) will be determined at the skin line on a true transverse view at the level of the junction of the umbilical vein, portal sinus, and fetal stomach when visible.
- Estimated fetal weight (EFW) will be obtained using a combination of measurements such as BPD, HC, AC and FL from previously described formulas, expressed in grams, and compared with weight percentiles from published nomograms.

Elements of the Fetal Anatomic Survey:

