- Head, Face and Neck: Cerebellum, choroid plexus, cisterna magna, lateral ventricles, midline falx, cavum septi pellucidi, third ventricle, corpus callosum, posterior fossa, cerebellum, transcerebellar diameter (in centimeters), profile, nose, nasal bone, orbits, lips and palate.
- Chest-Heart: Four-chamber view, outflow tracts, situs, fetal heart rate and rhythm.
- Abdomen: Stomach (presence, size and situs), kidneys, bladder, umbilical cord insertion into the fetal abdomen, umbilical cord vessel number.
- Spine: Cervical, thoracic, lumbar and sacral spine.
- Extremities: Legs and arms (presence or absence). Femoral and humeral length in centimeters. Other long bone lengths will be obtained as clinically indicated.
- Genitalia (male, female, ambiguous).

Fetal Biometry at Repeat Examination: (ultrasound for growth to be performed at 4 week intervals)

- BPD, HC, FL, HL, AC, EFW.
- Fetal presentation.
- Amniotic fluid index and/or amniotic fluid deepest vertical pocket.
- Placental position (placental position at the initial evaluation may not correlate with its location in the third trimester).

- Maternal cervix (cervical length will be measured transabdominally or transvaginally at each sonographic evaluation until 32 weeks gestation) and presence, location and size of uterine and adnexal masses.

Doppler Ultrasonography:

Doppler color flow mapping with reduced color scale will be used to identify the ductus venosus (DV) and the middle cerebral artery (MCA) and average color scale to locate the umbilical artery (UA) and maternal uterine arteries (UtA). Pulsed- wave Doppler will be used to determine blood flow velocities of the UA, UtA, DV and MCA. The peak systolic velocity, peak diastolic velocity, mean velocity, systolic to diastolic ratio (SD), pulsatility index (PI) resistive index (RI) and UA PI/MCA PI with a mixture from stable signals during fetal apnea will be obtained for each of the aforementioned vessels at the initial evaluation at 24-28 weeks and then every 4 weeks.

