In the secondary analyses, we will use an exact binomial confidence interval to estimate differences between groups in the percent of subjects with PVL pre-operatively and the rate of increase post-operatively. The null hypothesis that treatment does not reduce the frequency of occurrence of PVL pre-operatively and the rate of increase post-operatively will be tested using Fisher's Exact test. The confidence level will be set at 90% and the Type I error at 10%. The PVL data can also be modeled in a more unified approach using mixture models, where the categorical data for patients with no PVL, and the continuous data for patients with evidence of PVL are modeled jointly.⁸⁸ In addition to these analyses, we will describe compliance, both with treatment and with MRI tests, as well as determine loss to follow-up for the 18 month time point. We will secondarily model TMS, VMWM and the Bayley-III Cognitive and Language Scales as a function of treatment, as well as other potential predictors of fetal brain maturation and development including: gestational age, type of CHD, ethnicity, age at surgery, operative management variables, maternal education and socioeconomic status. Presence of 22q11 deletions or other identified genetic anomaly and apo-lipoprotein E (*APOE*) genotype will be included as covariates in the analysis of the Bayley-III scores.

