5. *Binary Secondary Endpoints* will use an exact binomial confidence interval to estimate differences between groups and will be tested using Fisher's Exact test. The confidence level will be set at 90% and the Type I error at 10%. Binary outcomes include
 - a. Presence of WMI pre- and post-operatively
 - b. Completion of MRIs
 - c. Completion of Bayley III at 18 months
6. *Per Protocol and As Treated*
 - a. The analyses of the primary and secondary endpoints described above will be repeated with alternatives to the intention to treat cohort.
 - b. A 'strict' *per protocol* analysis will be used, considering only those subjects who were eligible for the study and who received the treatment as specified in the protocol. This analysis will consider only those subjects who completed at least 90% of their doses at the time of study-based discontinuation (pre-planned at XX weeks or due to earlier labor and delivery). Adherence will be measured in two ways (1) number of medication doses returned and (2) mother's diaries of medication use. Differences in the two measures of adherence will be described.
 - c. As a sensitivity analysis, a 'relaxed' *per protocol* analysis will follow (a) but use completion of 80% of doses instead of 90% of doses, as the cut-off.
 - d. An *as treated* analysis will consider subjects based on their 'dose of progesterone' based on their assignment to control or intervention arm, as well as adherence to study drug in the progesterone arm. In this case we will include dose as a continuous covariate in a regression model, using linear regression for continuous outcomes or logistic regression for binary outcomes. We will assess interactions between dose and treatment arm. This analysis will estimate the effect of the treatment intervention conditional on different levels of adherence to study medication.

7. *Modeling to Adjust for Covariate Imbalance.* Linear or logistic regression analyses of the primary and secondary outcomes will be carried out with adjustment for baseline covariates of fetal brain maturation and development. The covariates will include type of CHD (primary cardiac diagnosis), race, ethnicity, maternal education and socioeconomic status, presence of 22q11 deletions, other identified genetic anomalies and (*APOE*) genotype.
8. Missing data and truncation by death

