 - a. In sensitivity analyses, multiple imputation will be used to impute missing outcome data using baseline covariates. Results will be compared to the primary analysis using the complete data.
 - b. Some subjects will have missing data for the 18-month endpoint due to truncation by death. In sensitivity analyses, we will assess the impact of this source of missingness using principal stratification.
9. Subgroup analyses of Primary & Pre-specified Secondary Endpoints:
10. Primary cardiac diagnosis
11. With versus without 22q deletions
12. With versus without any genetic anomaly
13. Males versus Female infants
14. Subjects undergoing surgical repair or not
15. With/without impaired maternal-fetal environment as defined above

Safety Analysis

All subjects the study at will be included in the safety analysis. The frequencies of adverse event (AE) by type, body system, severity and relationship to study drug will be summarized for both the mother and the neonate. Serious adverse events (SAE), if any, will be described in detail. AE incidence will be summarized along with the corresponding exact binomial 95% two-sided confidence intervals.

Further analyses anticipated for additional paper(s)

Using linear regression, we will assess the association between the neurodevelopmental outcomes with:

- 1) MRI findings (microhemorrhage, gray and white matter volumes, white matter injury (WMI) presence and volume, infarction, volume and growth trajectory) to neurodevelopmental (ND) outcomes
- 2) post-operative seizures
- 3) maternal complications and baseline clinical variables including diabetes, hypertension, smoking status, pre-eclampsia, hypothyroidism
- 4) placental findings
- 5) impaired maternal-fetal environment

Using regression techniques, including logistic regression for white matter injury (WMI) and competing risk time-to-event analyses (length of stay) with death as a competing risk), we will assess the association between the outcome (WMI, length of stay) and

- 1) maternal complications and baseline clinical variables
- 2) placental findings
- 3) trajectories of brain growth

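### The SAP's covariate-adjusted model (Efficacy Analysis, item 7) does not list infant sex, so a chance sex imbalance would stay in the adjusted overall difference; the likely effect is small

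*SAP*

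**What the plan says.** The primary analysis of the Bayley-III Motor Scale is an unadjusted two-sample t-interval and t-test at the 90% confidence level (SAP, Efficacy Analysis, item 1). Item 7 then adds linear or logistic models for the primary and secondary outcomes "with adjustment for baseline covariates of fetal brain maturation and development". The list is: "The covariates will include type of CHD (primary cardiac diagnosis), race, ethnicity, maternal education and socioeconomic status", then 22q11 deletion, other genetic anomalies and APOE genotype. Protocol section 6.3.2 has an earlier list of predictors, "gestational age, type of CHD, ethnicity, age at surgery, operative management variables, maternal education and socioeconomic status", and it does not name sex either.

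Sex appears elsewhere in the documents:

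- **Baseline.** Protocol 5.2.1 puts an anatomic survey in the first examination ("The detailed obstetric ultrasound examination to be performed at the initial evaluation will include cardiac activity", and so on through the survey). One entry in that survey is fetal sex: "Genitalia (male, female, ambiguous". Section 3.1.2 makes the obstetric ultrasound part of the baseline evaluation, which it describes before randomisation.
- **Birth.** Appendix 1 (post-natal record review) collects gender.
- **SAP, Descriptive Statistics, item 4.** Sex is one of the characteristics of the neonate.
- **SAP, subgroup list.** "Males versus Female infants" is a subgroup for the primary and pre-specified secondary endpoints.

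Randomisation is stratified by fetal cardiac diagnosis only (protocol 3.2.1 and 9.1.1).

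**The concern.** A model whose stated job is to deal with covariate imbalance should hold the baseline factors that the plan itself regards as relevant and already collects. Sex is such a factor. It cannot be affected by treatment, even when it is read from the birth record, and the design does nothing to balance it. The SAP thinks it worth a subgroup.

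As written, a chance excess of boys in one arm would pass into the adjusted overall difference just as it passes into the unadjusted one. The subgroup analysis gives separate contrasts in roughly half-size samples, not a sex-adjusted overall estimate. The descriptive table would show an imbalance, but adding sex to the model after seeing it would be a data-driven choice. Naming sex in advance avoids that.

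**Working it through.** **Inputs from the documents.** 40 evaluable infants per arm, SD 15 for the Motor Scale, a 90% two-sided interval, and a 6-point difference described as clinically relevant (protocol 6.4).

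**Inputs that are assumptions.** Half of the infants are male. The sex gap on the Motor Scale is 0 to 6 points (0 to 0.4 SD). Neither figure is in the documents.

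**1. The plan's own precision.** SE = 15 × √(2/40) = 3.35. Half-width = t(0.95; 78 df) × SE = 1.665 × 3.354 = 5.58, which matches the 5.6 in section 6.4.

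**2. How often sex is imbalanced by chance.** Take the number of males in each arm as binomial (n, 0.5), independent between arms. At 40 per arm the SD of the difference in proportion male is √(2 × 0.25/40) = 0.112, or 11.2 percentage points. Summing the exact probabilities:

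| Infants per arm | P(difference ≥ 10 points) | P(difference ≥ 20 points) |
|---|---|---|
| 40 | 0.434 | 0.093 |
| 60 | 0.315 | 0.035 |

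The row for 60 per arm corresponds to the number expected at the pre-operative MRI.

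**3. How far an imbalance moves the Motor difference.** Shift = sex gap × difference in proportion male.

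| Assumed sex gap (points) | Shift at 10-point imbalance | Shift at 20-point imbalance | 20-point shift ÷ SE of 3.35 |
|---|---|---|---|
| 0 | 0 | 0 | 0 |
| 3 | 0.3 | 0.6 | 0.18 |
| 6 | 0.6 | 1.2 | 0.36 |

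Against the 6-point difference, the shifts of 0.6 and 1.2 are 10% and 20%. Against the planned half-width of 5.6 they are about 11% and 21%.

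**4. Precision gained by adding sex (balanced case).** R² = gap² × 0.25/225. Residual SD = 15 × √(1 − R²). Half-width = t(0.95; 77 df) × residual SD × √(2/40).

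| Assumed sex gap (points) | R² | Residual SD | Half-width |
|---|---|---|---|
| 0 | 0 | 15.00 | 5.58 |
| 3 | 0.01 | 14.92 | 5.56 |
| 6 | 0.04 | 14.70 | 5.47 |

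The lost degree of freedom is negligible, since the half-width at a zero gap is still 5.58. The gain at the top of the assumed range is about 2% (5.47/5.58 = 0.98).

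**5. Maternal education beside socioeconomic status.** Protocol 5.1.6 collects education and employment on both parents and says: "This information will serve as data to calculate the Hollingshead score, a measure of SES". The two covariates therefore overlap. A simulation with 80 subjects, 3,000 runs per setting and an assumed correlation of 0.6, 0.8 or 0.9 between them (variance inflation 1.6 to 5.3) compared models with and without education. The treatment estimate changed by no more than 0.02 points on average, and its standard error stayed at 3.15 to 3.16 in both models.

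**The case against.** The strongest reply is that nothing in the plan becomes invalid. The primary analysis is the unadjusted t-interval, randomisation keeps it unbiased over repeated trials, and its standard error already allows for chance imbalance in every unlisted factor, sex included. Item 7 is supportive, its wording may not be meant as exhaustive, no model can hold every prognostic factor, and the trial is an exploratory one aimed at estimation. All of that stands, and it is why the point is minor. It does not explain why a known and already collected baseline factor is left out of the one model meant for imbalance.

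Some stronger readings are tempting but not supported:

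- **That the documents show sex to matter for the Bayley score.** Protocol 1.3.2 says the neuroprotective effect was noticed through "sex differences in recovery from experimental brain injury". That is the history of the discovery. The same section goes on to relate the effect to brain development in both sexes. At most this suggests that sex could modify the treatment effect, which the subgroup addresses. It does not show that sex predicts the outcome, which is what adjustment needs. If the gap is zero, the shift is zero.
- **That sex plays no part in any comparison of the arms.** The subgroup compares the arms within each sex for the primary and pre-specified secondary endpoints. What is missing is a sex-adjusted overall comparison.
- **That fetal sex will be known at baseline for every dyad.** The survey allows an ambiguous result, the visit lists in protocol 4.1.1 and 4.1.2 do not name the obstetric ultrasound, and study drug may be started off site. The birth record is the safer source.
- **That maternal education is counted twice and should be dropped.** The SAP does not name its socioeconomic measure. The Hollingshead score draws on both parents' education and employment, so it is not the same variable as maternal education. The overlap blurs the coefficients of those two covariates, not the treatment effect.

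**Conclusion.** The omission is real but small. Item 7 cannot remove a chance sex imbalance from the adjusted overall difference, because sex is not in it. At 40 per arm an imbalance of at least 10 points arises in 43% of trials and one of at least 20 points in 9%, if half of the infants are male. For the Motor Scale, a 20-point imbalance would shift the difference by 0 to 1.2 points over an assumed sex gap of 0 to 6 points, which is well inside the planned interval. The half-width would improve at best from 5.58 to about 5.47. The size rests wholly on the assumed gap, and it could be larger or smaller for other outcomes such as brain volumes or growth, for which the documents again give nothing. The primary analysis is not in question.

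**What to change.** Add infant sex to the item 7 covariate list for all outcomes, taken from the birth record with the baseline ultrasound as back-up, or state why it is left out. Keep maternal education and socioeconomic status as they are, since dropping either has no demonstrated gain.

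The cost is one term in the SAP text and one model degree of freedom. No new data are needed. In the logistic models, where events may be few, an extra term weighs more than in the linear ones, but that concerns the length of the whole list rather than sex in particular.

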3.1.2 In Utero Treatment Phase

After informed consent is obtained, the subject will undergo baseline evaluation including medical history review, physical examination, obstetric ultrasound, fetal echocardiography, and fetal brain MRI. Maternal and paternal blood samples will be obtained. Progesterone levels will be assessed in the mother. Serum samples will be banked for later assessment of progesterone metabolites and biomarkers. The maternal and paternal samples will be used for genetic testing. Subjects will be randomized to study drug or placebo. For scheduling reasons, off site SD initiation may occur. After randomization, the subjects will return for routine prenatal visits every 2 weeks until 36 weeks GA and weekly thereafter. Obstetric ultrasound and fetal echocardiography will be performed every 4 weeks and as clinically indicated. Maternal blood tests will be repeated every 4 weeks. Fetal brain MRI will be obtained at 34-36 weeks GA. The study drug will be continued until 39 weeks GA, the onset of spontaneous labor if prior to 39 weeks GA, or the time of induction of labor or cesarean section for maternal or fetal health concerns. At the time of delivery, maternal and cord blood samples will be obtained. A portion of the placenta will be obtained.

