Statistical Analysis Plan
Randomized Trial of Maternal Progesterone Therapy to Improve
Neurodevelopmental Outcomes in Infants with Congenital Heart Disease.

J. [name], Principal Investigator
[name], PhD, ScD, Statistician

ClinicalTrials.gov identifier (NCT number): [NCT02133573](#)

Sponsor: Children's Hospital of Philadelphia

Version Date: 3/7/2022

Design: Randomized phase II 2-arm trial design

Control: Vaginal lubricant, twice a day

Intervention: Vaginal gel, 90mg twice a day

Consort Diagram: Per recommendations. <http://www.consort-statement.org/consort-statement/flow-diagram>

Primary Endpoint

The primary endpoint is the Motor Scale of the Bayley-III at 18 months of age.

Secondary Endpoints (Pre-specified in the protocol)¹

Secondary endpoints pre-specified in the protocol are:

1. Developmental (Bayley-III at 18 months of age)
 - a. Cognitive Scales
 - b. Language Scales
 - c. Fine motor score
 - d. Gross motor score
 - e. Receptive Communication
 - f. Expressive Communication
2. Adherence to study protocol
 - a. Progesterone regime (Average adherence by medication return and by diary)
 - b. Complete pre- and post-natal MRI's
 - c. Complete 18-month neuro-developmental evaluation
3. MRI-based
 - a. Total maturation score (TMS) on Pre-operative MRI
 - b. Brain volumes on Preoperative MRI:
 - i. Whole Brain
 - ii. Cerebellum
 - c. White Matter Injury
 - i. Volume on early post-natal brain MRI
 - ii. Volume on early post-operative brain MRI
 - iii. Volume change from pre-operative to post-operative brain MRI.

‘Secondary’ endpoints (Post Protocol) As clinical practice and research findings regarding progesterone use during pregnancy evolved over the course of accrual to the trial, these new secondary endpoints were identified. They were prespecified prior to closure of the database, and while the principal investigator and research team, other than [name] and [name] (statistical analyst), were blinded. They include;

1. Fetal Variables: Fetal echocardiogram and OB ultrasound Doppler flows (umbilical artery, uterine artery, middle cerebral artery, oligohydramnios, fetal growth restriction (BW < 10th percentile))
2. Maternal Complications: (gestational hypertension, preeclampsia, abruption, , gestational DM, maternal tobacco use, maternal hypothyroidism)

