¹ We anticipate the trial resulting in at least two publications related to endpoints. In advance of seeing the unblinded data we anticipate a publication describing in depth results related to the primary endpoint and adherence. A brief description of key MRI-based endpoints may be included. A second publication will focus on MRI-based endpoints.

3. Impaired maternal-fetal environment (presence of 1 or more of gestational hypertension, preeclampsia, gestational DM, maternal tobacco use, maternal hypothyroidism)
4. Delivery Complications (abruption, post-partum bleeding, DVT/PE, perinatal mood/anxiety disorder, wound complications (infection, breakdown))
5. Postmenstrual age of neonate at time of birth,
 - a. Categorical: born earlier than 37 weeks postmenstrual age (PMA)
 - b. Continuous: PMA
6. Type of Delivery (Vaginal, Elective C-section, Emergent C-section)
7. Birthweight (BW), absolute and as Z-score
8. Placental descriptors: (placental weight (PW), PW < 10th percentile, ratio of BW to PW, presence of infarction, fetal vascular malperfusion, maternal vascular malperfusion, fetal vascular thrombi).
9. Brain growth and development. Trajectories of total and regional brain volumes and TMS from fetal to first post-natal MRI,
10. Post-operative seizures
11. Microhemorrhage and infarction
12. Age at post-operative MRI
13. Operative management variables (Cardiac operation during first admission y/n, age at first operation, cardiopulmonary bypass (CPB) y/n, weight at first operation, Clancy class, , deep hypothermia circulatory arrest (DHCA) time, Total support time (TST), antegrade cerebral perfusion time, need for extracorporeal membrane oxygenation (ECMO), additional operations with CPB, additional TST, additional DHCA)
14. Mortality (in-hospital, on-study and post-study)
15. Length of stay and selected complications for first surgical admission
16. Weight, length and HC at 18 months, absolute and as WHO percentile and Z-score

Intention to Treat Principle Unless otherwise specified, all analyses are conducted on an ‘as-randomized’ basis, irrespective of adherence to treatment. This analysis follows the intention to treat principle pre-specified in the protocol.

Descriptive Statistics (Intention to treat cohort)

1. Analyses will be done for the overall cohort as well as by primary cardiac diagnosis (HLHS, TGA, Other).

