2. Baseline characteristics of mother: Using descriptive statistics (as appropriate, means median, number of subjects, proportion, standard deviation (SD), interquartile range (IQR)) to summarize demographic (Age of mother, race, ethnicity, education level of parents, clinical characteristics of mother) and clinical characteristics (Primary cardiac diagnosis, time to surgery, whether surgery was carried out) of the study cohort overall and by arm. Assess rates of missing data in baseline characteristics.
3. Determine rates of completion of primary endpoint of the study by arm. Describe causes of attrition including death (by arm). Kaplan-Meier plots of time-to-death by arm while on-study.
4. Characteristics of neonate. Type of birth (vaginal, emergency cesarean, planned cesarean), complications of pregnancy, progesterone level in cord blood, postmenstrual age of neonate, birthweight, sex, genetic anomaly, apo-lipoprotein E (*APOE*) genotype
5. Primary & secondary outcomes. These outcomes will be described using summary statistics, and for continuous variables, graphically to visualize the distribution, overall and by arm.

6. Genetic anomalies. The protocol pre-specified inclusion of 22q11 individuals. Additional anomalies as genomic information has evolved will be described. Subjects will be classified as Abnormal, Suspect, or Normal based on examination by a dysmorphologist and genetic testing (WES, microarray, and other clinical testing). Subjects with 22q11 deletions will be classified as Abnormal.

Efficacy Analysis

1. *Primary Endpoint (Motor Scale, Bayley III)*. The analysis will use a two-sided two-sample T-interval (estimation) or T-test (hypothesis testing). The confidence level will be set at 90% and the Type I error at 10%.
2. Normality will be assessed. A transformation, or alternatively a non-parametric test, will be used as appropriate.
3. Sensitivity of results to diagnosis group will be assessed by including diagnosis group as a stratification variable in a linear regression model.
4. *Continuous Secondary Endpoints* using the same analysis as the primary endpoint:
 - a. Cognitive and Language Scales (Bayley III)
 - b. TMS
 - c. Brain volumes
 - d. WMI volumes
 - e. PVL volumes
 - f. Adherence to study drug

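### Two planned treatment-effect subgroups, surgical repair and impaired maternal-fetal environment, are settled wholly or partly after randomisation and also feature among the trial's outcomes

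*SAP*

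**What the plan says.** The SAP, Efficacy Analysis, item 9 announces subgroup analyses of the primary and pre-specified secondary endpoints, and items 10 to 15 list the factors. Two matter here: item 14, "Subjects undergoing surgical repair or not", and item 15, "With/without impaired maternal-fetal environment as defined above".

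The definition that item 15 points back to is item 3 of the post-protocol secondary endpoints: "Impaired maternal-fetal environment (presence of 1 or more of gestational hypertension, preeclampsia, gestational DM, maternal tobacco use, maternal hypothyroidism". Most of its components also appear in item 2 of that list, "Maternal Complications: (gestational hypertension, preeclampsia, abruption" and others. No onset window is given in either place.

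Item 13 of the same list makes a close relative of the surgery factor an endpoint: "Operative management variables (Cardiac operation during first admission y/n". Yet Descriptive Statistics, item 2, headed as baseline characteristics of the mother, includes "clinical characteristics (Primary cardiac diagnosis, time to surgery, whether surgery was carried out) of the study cohort overall and by arm".

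On timing, Protocol 3.1.1 and 3.3.1 put screening and the start of participation at 24-28 weeks, and Protocol 3.1.2 says "The study drug will be continued until 39 weeks GA", or to labour or delivery if earlier.

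The SAP does address one kind of post-randomisation selection. For truncation by death (item 8b), "we will assess the impact of this source of missingness using principal stratification". It has nothing similar for entry to the subgroups in items 14 and 15.

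**The concern.** A subgroup treatment comparison keeps the protection of randomisation only if membership is fixed before treatment or cannot be altered by it. Surgery fails the first condition outright. The composite fails it in part: tobacco use and hypothyroidism can predate randomisation, and the diabetes screen falls at 24-28 weeks (Protocol 5.1.5), but gestational hypertension and preeclampsia can arise on study drug.

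The resulting problem is selection bias, and it needs two links: the arm must affect entry, and the risk that drives entry must relate to the Bayley score. The SAP leaves the first open by listing the composite as a trial endpoint. It treats the second as plausible, because its section on further analyses plans to relate neurodevelopmental outcomes to maternal complications and to the impaired environment. If both hold, a drug that prevents the complication leaves a higher-risk group of treated infants in both strata, and so can look harmful in both with no effect on Bayley score.

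The trial is meant to inform a multi-institutional study (Protocol 2), so a false subgroup signal could carry into that design. Placing surgery among baseline characteristics makes such a misreading more likely.

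**Working it through.** **1. The plan's own figure.** Protocol 6.4 gives a 90% half-width of 5.6 points for 40 per arm and SD 15. The formula is t(0.95, n1+n2−2) × 15 × √(1/n1 + 1/n2). With 40 v 40 it gives 5.58, so the figure reproduces.

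**2. Timing of each factor.**

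| Factor | When settled | Also listed as |
|---|---|---|
| Tobacco use, hypothyroidism | can predate randomisation | post-protocol endpoints |
| Gestational diabetes | screened at 24-28 weeks, the randomisation window | post-protocol endpoint |
| Gestational hypertension, preeclampsia | can arise on study drug | post-protocol endpoints |
| Surgery or not | after birth | close variant is an endpoint; also listed as baseline |

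**3. Size of a possible bias, composite split.** The documents give neither a prevalence nor a correlation, so these are assumptions. Let L be a standard normal latent risk whose correlation with Bayley score is −r. An infant enters the subgroup when L exceeds a cut c that depends on arm, with P(L > c) = p. There is no drug effect on Bayley score. Then E[L | in] = φ(c)/p and E[L | out] = −φ(c)/(1−p). The false difference, treated minus control, is −15 × r × (gap in E[L]).

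- 30% control v 20% treated. In: 1.400 − 1.159 = 0.241. Out: −0.350 + 0.497 = 0.147.
- 40% control v 25% treated. In: 1.271 − 0.966 = 0.305. Out: −0.424 + 0.644 = 0.220.
- Equal entry in both arms: gap 0, bias 0.

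For example, at r = 0.5 and 40% v 25%, the 'with' stratum gives 15 × 0.5 × 0.305 = 2.3 points. Subgroup sizes below apply the percentages to 40 per arm, control v treated. The false-positive rate is for a two-sided 10% test, from the noncentral t with SD held at 15.

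| Entry | Stratum | n | 90% half-width | r | Treated appear lower by | % of half-width | False-positive rate |
|---|---|---|---|---|---|---|---|
| 30% v 20% | with | 12 v 8 | 11.9 | 0.2 | 0.7 | 6% | 10.2% |
| | | | | 0.5 | 1.8 | 15% | 11.1% |
| | without | 28 v 32 | 6.5 | 0.2 | 0.4 | 7% | 10.2% |
| | | | | 0.5 | 1.1 | 17% | 11.3% |
| 40% v 25% | with | 16 v 10 | 10.3 | 0.2 | 0.9 | 9% | 10.4% |
| | | | | 0.3 | 1.4 | 13% | 10.8% |
| | | | | 0.5 | 2.3 | 22% | 12.3% |
| | without | 24 v 30 | 6.9 | 0.2 | 0.7 | 10% | 10.4% |
| | | | | 0.3 | 1.0 | 14% | 11.0% |
| | | | | 0.5 | 1.7 | 24% | 12.7% |

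A simulation of the same model with 2 million subjects (40% v 20%, r = 0.3) gave −1.96 and −1.32 points in the two strata and 0.00 overall. The bias comes from the split, not from the as-randomised comparison.

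**4. Surgery split.** Protocol 3.4.1 requires a defect needing bypass surgery before 44 weeks corrected gestational age, so few infants should go unoperated. If 10% did (assumed), 4 v 4 infants give a half-width of 1.943 × 15 × √(1/4 + 1/4) = 20.6 points. Protocol 3.1.3 ties both postnatal MRIs to surgery, one on the day and one within 10 days after. Unoperated infants would therefore largely lack the MRI endpoints to which item 9 also applies this split.

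**The case against.** The strongest reply is about weight. The primary analysis is untouched, the trial is exploratory, and no decision in the SAP hangs on these subgroups. Even the worst assumed case moves a 10% test only to 12.7%. All of that stands.

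The scenarios may also be generous. If half of the control-arm composite were pre-existing conditions that the drug cannot change, 40% v 25% would mean the rest falling from 20% to 5%, a 75% relative reduction; 30% v 20% would mean 15% to 5%, or 67%. Nothing in the documents suggests effects of that size, so the table should be read as illustration.

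For surgery, no mechanism by which progesterone would change who is operated on has been shown, and the 20.6-point half-width measures imprecision, not bias. The endpoint, operation during the first admission, is also close to the subgroup variable but not identical. These points stand too. They do not make surgery a baseline variable in a trial that randomises in utero.

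Descriptive Statistics, item 2 already reports surgery by arm, and the adjustment covariates in item 7 include neither surgery nor the composite. The listing fault is therefore one of heading and does not contaminate the adjusted models. Finally, restricting the composite to pre-randomisation components changes what it measures. That is a real cost.

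**Conclusion.** The concern holds. Items 14 and 15 would present, as subgroup treatment effects, contrasts on factors not fixed at randomisation, with no onset limit, caution or causal method. Surgery is wholly post-randomisation and is misplaced among baseline characteristics; that part needs no assumption.

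Bias is conditional: zero if entry does not depend on arm or if the risk driving entry is unrelated to Bayley score. The documents give no evidence either way on the effect of progesterone on entry in these pregnancies. Under the assumed entry rates and correlations of −0.2 to −0.5, it is 0.4 to 2.3 points, small beside subgroup half-widths of 6.5 to 11.9 points. No bias has been estimated for the surgery split. The case for change rests on validity and correct labelling at low cost, not on a large numerical distortion.

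**What to change.** - **Item 15:** for the treatment-effect subgroup, count a component of the composite only if it was documented before randomisation. Keep the full composite as an outcome.
- **Item 14:** report surgery done or not descriptively by arm, and drop it as a treatment-effect subgroup.
- **Descriptive Statistics, item 2:** move whether surgery was carried out, and time to surgery, out of the baseline characteristics.
- **If either split is kept as written:** state that it is non-randomised and descriptive.

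The cost is a few lines of SAP wording and a check of dates in the maternal data. Appendix 1 of the Protocol lists antepartum complications and smoking without naming onset dates, so it should first be confirmed that those dates can be recovered. The restricted 'impaired' subgroup will be smaller and will rest mainly on tobacco use, hypothyroidism and some gestational diabetes. If that is not useful, the label alone costs one sentence and loses no data.
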